# 9.2 Risks of Everolimus, TAC, MMF, and Prednisone

TAC, MMF, and prednisone are considered standard of care maintenance IS medications in liver transplantation. EVR is not as widely used in liver transplantation but recently received an FDA-approved indication for liver transplantation. The risks for dose related toxicities and side effects from these immunosuppressive medications are not different for subjects in this trial. However, the reduced dosing or target trough levels in conjunction with other agents in the Treg-supportive IS regimen may expose subjects to an increased risk of rejection.

# 9.3 Risks of darTreg Infusion

### 9.3.1 Risks of autologous ex vivo expanded polyclonal Treg infusion

Although polyclonal Treg infusion has been innocuous in animal models, there is currently scant experience in humans. Three Treg therapy trials in GvHD have been reported. The first-in-man trial by Trzonkowski et al involved two patients (Trzonkowski, 2009). The first patient had chronic GvHD two years after transplantation. After receiving 0.1 x 10^6/Kg flow sorted ex vivo expanded Tregs from the donor, the symptoms subsided and the patient was successfully withdrawn from IS. The second patient had acute GvHD disease that progressed despite three infusions with an accumulative dose of 3 x 106/Kg expanded donor Tregs. A larger scale phase I trial led by Brunstein et al (Brunstein, 2010) enrolled twenty three patients with advanced hematologic malignancy. The patients were treated with two units of umbilical cord blood as source of stem cells and effector T cells. Tregs were isolated using anti-CD25 immunomagnetic bead selection from thirdparty cord blood samples that had 4 to 6 HLA match with the recipient. Up to 6 x 10^6/Kg Tregs were infused after ex vivo expansion using anti-CD3 and anti-CD28 conjugated beads. The infused Tregs were detectable in circulation for up to 7 days. During the one-year period after Treg infusion, the investigators observed no DLTs and AEs when compared to historical controls. Incidences of acute and chronic GvHD were reduced in patients received Treg therapy. The third trial enrolled 28 patients with high-risk hematological malignancies (Di lanni, 2011). Patients received anti-CD25 immunomagnetic bead enriched donor Tregs without ex vivo expansion four days before receiving one haplo-mismatched hematopoietic stem cell and Tconv transplants from the same donors. A majority of the patients received  $2 \times 10^6 / \text{Kg}$  Tregs with 1 x 10^6/Kg Tconvs and no adjunct IS was given after transplant. Patients demonstrated accelerated immune reconstitution, reduced CMV reactivation, low incidence of tumor relapse and GvHD. Collectively, these studies show that Treg therapy has minimal toxicity in the setting of GvHD.

Recently, a phase I/II study applying polyclonally expanded FACS purified Tregs to type diabetic patients has been reported by the Trzonkowski group (Marek-Trzonkowska N, 2012). The study enrolled 10 type 1 diabetic children (aged 8-16 years) within 2 months after diagnosis. Four patients received  $10 \times 10^6$  Tregs/kg body wt and the remaining 6 patients received  $20 \times 10^6$  Tregs/kg body wt. The patients were followed for 4-5 months after Treg infusion and no toxicity of the therapy was noted. The authors concluded that Treg therapy was safe and well tolerated in children.

At UCSF, a phase I Treg dose-escalating trial evaluating safety of Treg therapy in type 1 diabetic patients is ongoing. As of January 23, 2013, 10 enrolled subjects have received a single infusion of Tregs. Three subjects were treated in the first dosing cohort with 0.05x10^8 cells, three subjects were treated in the second dosing cohort with 0.4x10^8 cells, and four subjects were treated in the third dosing cohort with 3.2x10^8 cells. Notably, two of these 4 subjects were enrolled at treated at Yale (New Haven, Connecticut). Thirty-four AEs have been reported in these subjects. All 6 subjects in Cohorts 1 and 2 had at least one adverse event. Twenty-eight events were judged as mild in severity, three were judged as moderate, and three were judged as severe. Sixteen were judged to be possibly related, four unlikely related and 14 unrelated to study therapy. No SAEs have been reported. No events that would disallow dose escalation have occurred. The Data Safety and Monitoring Board will be reviewing the data in accordance with the protocol plan to determine if the study can proceed to enroll the final cohort that will receive a cell dose of 26 x10^8 cells in four subjects.

#### 9.3.2 Risks of autologous ex vivo expanded darTregs infusion

There is limited experience in humans using the darTreg product. Because infusion of *ex vivo* explanded effector T cells has been reported to be associated with infusion reactions, recipients of arTregs should be closely monitored after infusion

Confidential Page 47 of 80

for possible infusion reactions including nausea, hypotension, fevers, chills, and pain. Since the arTreg product is immunosuppressive, possible side effects include over-immunosuppression with increased risks of infections and difficulty clearing infections.

A safety concern of Treg infusion is potential impairment of immune responses to pathogens and/or malignancies. darTregs utilized in this trial are unlikely to possess the full breadth of specificities offered by non-specific, polyclonal Treg pool. Moreover, animal studies suggest that adoptive transfer of alloantigen-specific Tregs does not alter immune responses to viral pathogens (Bushell, 2005). The infusion of Tregs could theoretically impair anti-tumor immunity, which could be of particular concern in transplant recipients at increased risk of PTLD and/or recurrent HCC. With the infusion of darTregs, there is a theoretical possibility that donor reactive T effector cells may be infused and contribute to rejection.

Lastly, an ancillary reagent used in the manufacturing of darTreg is a CD40L-expressing cell line, KT64.CD40L.HLADR0401, which is derived from the human myelogenous leukemia cell line K562. These cells have been irradiated 10,000 rads (5 times the lethal dose); they are therefore not expected to persist in darTreg cultures. To further prevent the infusion of replication competent K562 cells along with the darTregs, the final darTreg product must meet a release criterion of a negative assay for the BCR-ABL translocation, a genetic marker identifying K562 cells. The risk of transmission of myelogenous leukemia in the Treg product is considered to be negligible.

Possible adverse reactions include, but are not limited to, abdominal cramps, anaphylaxis, back pain, chest tightness/pain, and/or chills at the time of infusion, fever ≤38.5°C, flashing, heat/pain at the IV site, hemoglobinuria, hives, mild rigors, nausea, headache, oliguria, pruritus, sever rigors, syncope, tachycardia, vomiting, and wheezing.

Confidential Page 48 of 80

# 9.4 Risks of Study Mandated Procedures

### 9.4.1 Risks of Leukapheresis

The common risks of leukapheresis include bruising and discomfort at the site of needle placement, typically in the antecubital fossae. Calcium level in blood may fall due the citrate anticoagulant used to prevent clotting in the leukapheresis instrument. Hypocalcemia can lead to perioral or digital numbness and tingling. Calcium replacement may be used during the procedure and is routinely used at the conclusion of the procedure. Platelet count may fall due to platelet loss during processing. Hemorrhagic complications due to thrombocytopenia have not been reported in normal donors. Our inclusion/exclusion criteria specify a minimum acceptable platelet count for participants. Thrombosis and bleeding could theoretically occur, although they are rarely if ever observed.

#### 9.4.2 Risks of Blood Draw

Risks of blood draw or venipuncture are typically minimal with temporary local discomfort. More serious risks would include ecchymosis and, rarely, localized infection. The amount of blood that may be drawn from adult subjects for research purposes will not be more than 168 mL over an eight-week period. The additional amount of blood could contribute to the development of anemia. The subject's clinical condition will be taken into consideration to determine if research blood tests can be performed.

# 9.4.3 Risks of Liver Biopsy

Mild AEs resulting from a liver biopsy include local pain during and for a short period of time (hours or at most days) after the procedure that will be experienced to some degree by every participant. The second adverse event that is typically of mild to moderate severity is bleeding. Although some bleeding likely occurs with every biopsy, it typically does not result in any symptoms; the only sign might be a small decrement in hemoglobin / hematocrit. More serious bleeding after a liver biopsy is typically diagnosed by a significant drop in the hemoglobin / hematocrit that does not cause any symptoms. The risk of requiring a transfusion secondary to excessive bleeding is 0.5 to 1% (Rockey, 2009). Even rarer would be symptomatic hemorrhage and/or the requirement for operative or other procedural intervention to stop bleeding.

Other potentially serious risks associated with liver biopsy include pneumothorax or colonic perforation. If either were to occur, hospitalization as well as procedural or operative intervention may be necessary. Finally, there is a very small risk of death after liver biopsy, estimated at 0.1 to 0.01% (Rockey, 2009).

#### 9.5 Potential Benefits

This study provides no direct or immediate benefit to the participants. However, the results of the study could influence future care of transplant patients.

Confidential Page 49 of 80

# 10. Study Visits

# 10.1 Stage 1: Screening, Enrollment and PBMC Collection

The first stage of the study encompasses screening A and enrollment. Participants will be selected from the liver transplant waiting lists according to the study eligibility criteria (Screen A). The research study will be explained in lay terms to each potential research participant by the site PI or designee listed on FDA form 1572. The potential participant will sign an informed consent form before undergoing any screening or study procedures. Surrogate consent will not be permitted. Once the informed consent form has been signed, the participant will be assigned a unique participant number. All screening procedures will be completed to ensure that the subject meets inclusion criteria and exclusion criteria A (Section 4.2 and 4.3.1).

Eligible and consented participants enrolled in Cohort 2, 3, or 4 will undergo leukapheresis (or blood draw option for Cohort 2) at any time prior to transplantation to isolate PBMCs, which will be cryopreserved for subsequent Treg purification and expansion. Participants who have detectable HBV DNA at the time of PBMC collection will be terminated from the trial. At the time of transplantation, donor material for these participants will be collected to make donor sBcs and banked to support future expansion of darTregs.

At the time of transplantation, participants will receive Solumedrol, 500 mg intravenously. Within 24 hours after transplantation, participants will be started on MMF in the form of either Cellcept 500mg bid intravenously or orally or Myfortic 360 mg bid by mouth. Within 72 hours after transplantation, participants will be prescribed tacrolimus to target 12-hour trough levels of  $6-8~\mu g/L$ . Please refer to *Appendix 1. Recipient Schedule of Events (Stages 1 and 2)*. Note that collection of AEs and SAEs in Stage 1 are limited to events occurring within 72 hours after leukapheresis.

# 10.2 Stage 2: Thymoglobulin® and TAC- or EVR-based Maintenance IS

The second stage of the study begins after liver transplantation with administration of Thymoglobulin®. The first dose must be initiated within 72 hours of transplantation (*Appendix 1. Recipient Schedule of Events (Stages 1 and 2*). Prior to Thymoglobulin® administration, enrollment inclusion criteria (*Section 4.2*) should be re-reviewed to ensure eligibility. In addition, exclusion criteria B (*Section 4.3.2*) should also be reviewed prior to administration of Thymoglobulin®. Note that collection of AEs and SAEs in Stage 2 begins with Thymoglobulin® administration.

Between 5-6 weeks after transplantation, participants who continue to meet study eligibility Screen C1 (Section 4.3.3) will be assessed by everolimus conversion criteria C2 (Section 4.3.4) will initiate conversion to an EVR-based IS regimen. EVR should be initiated at a dose of 1.0-1.5 mg bid, targeting 12 hour trough levels of 6-8  $\mu$ g/L no earlier than 30 days after liver transplantation. As EVR is introduced, both MMF and tacrolimus dosing should be reduced. MMF should be completely discontinued when target EVR levels are achieved. Tacrolimus should be reduced to target 12-hour trough levels of 3-5  $\mu$ g/L.

During Stage 2, study assessments will take place daily during administration of Thymoglobulin®. Starting at week 2, study assessments will occur weekly until 12 weeks after transplantation. Participants will have assessments at weeks 2, 3, 4, 6, 8, and 10 after transplantation. Participants enrolled in Cohorts 2, 3, and 4 must undergo an allograft biopsy between week 10-14 after transplantation as part of the eligibility determination for darTreg infusion (*Appendix 1. Recipient Schedule of Events (Stages 1 and 2) and Appendix 3*).

Participants in Cohort 1 (1a and 1b) should undergo an allograft biopsy 12 weeks after transplantation.

# 10.3 Follow-up for Cohorts 1a and 1b

Participants enrolled in Cohorts 1a and 1b who will not receive darTreg infusion will follow Appendix 2. Recipient Schedule of Events (Cohort 1a and 1b) starting at week 12 after transplantation. Visits to the transplant center will take place at week 12, 16, 24 and 40 after transplantation. Laboratory assessments will take place every 4 weeks until the end of the study, 40 weeks after transplantation. Please refer to Appendix 2. Recipient Schedule of Events (Cohort 1a and 1b Follow Up)

Confidential Page 50 of 80

### 10.4 Stage 3: darTreg Infusion for Cohorts 2, 3, and 4

Participants enrolled in Cohorts 2, 3, and 4 must undergo the following study procedures and visits. darTreg infusion will take place between weeks 11-20 after liver transplantation and will require an overnight stay. Screen D eligibility must be met. Blood for central laboratory assessments will be drawn prior to the infusion and 24 hours after the infusion is complete. Visits to the transplant center will take place 1 week and 4 weeks after darTreg infusion as well as 12 and 28 weeks after darTreg infusion (approximately 24 and 40 weeks after transplantation, respectively). A liver biopsy will be done in conjunction with the visit 1 week after darTreg infusion. Thereafter, laboratory assessments must take place every two weeks for 10 weeks, followed by every 4 weeks until the end of the study, 28 weeks after darTreg infusion, or 40 weeks after transplantation. Details regarding study procedures including monitoring, laboratory assessment, and blood draws for mechanistic studies are specified in *Appendix 1. Recipient Schedule of Events (Stage 3: Cohorts 2, 3, and 4)*.

#### 10.5 Unscheduled Visits

Unscheduled or additional visits will typically occur secondary to standard of care management for liver transplant recipients or secondary to concern for allograft dysfunction when there are liver tests that are elevated above baseline. Abnormal liver tests should be assessed according to center standard of care protocols. A liver biopsy should be performed to confirm any clinical suspicion of rejection prior to the administration of any treatment for rejection. In addition to research specimens, local pathology results generated with unscheduled visits will be collected for the study.

Local laboratory assessments recorded for the study at the time of clinically indicated biopsy should reflect reason for biopsy (e.g. elevated LFT's). Blood for mechanistic assays are not required unless the unscheduled visit coincides with a scheduled visit with central laboratory assessments.

### 10.6 Safety Follow Up

Subjects who are in Stage 2 or 3 and discontinue the study prematurely will be followed according to the safety follow up SOE (See Section 13.4, Appendix 4. Recipient Safety Follow Up (Early Termination from Stage 2) and Appendix 5. Recipient Safety Follow Up (Early Termination from Stage 3).

### 10.7 Visit Windows

Study visits should take place within the following time limits shown in Table 2. Study Visit Windows

### **Table 3. Study Visit Windows**

Stage 1 and 2 Study Visits	Visit Window
Screen A	-6 Months
Visit 1: PBMC Collection for darTreg manufacturing	Prior to transplant
Visit 2: Transplantation	-24 hours Central labs can be
	drawn up to 1 year before
	solumedrol dose in OR
Screen B	-24 hours before first dose
Visits 3a, 3b, 4, 5a, 5b: Days 3, 4, and 5 after transplantation	None
Screen C and Visits 6-15, 15a, 15b: Weeks 2-13 after transplantation	± 2 days
Cohort 1 Follow Up Study Visits	Visit Window
Visits 16: Week 12 after transplantation	-14/+10 days
Visits 17-23: Months 4-9 after transplantation	± 5 days
Stage 3 Study Visits	Visit Window
Screen D	-10 days
Visit T0: Day of darTreg Infusion	None
Visit T2: Day 1 after darTreg Infusion	± 1 hour
Visit T3: Day 7 after darTreg Infusion	± 1 day
Visit T4-T5: Day 14 and 28 after darTreg Infusion	± 2 days
Visits T6-T13: Weeks 6, 8, 10, 12, 16, 20, 24 and 28 after darTreg Infusion	± 5 days
Safety Follow Up (Early Termination from Stage 2 or 3)	Visit Window
All visits	± 7 days

Confidential Page 51 of 80

# 11. Mechanistic Assays

### 11.1 HLA Typing

DNA will be isolated from whole blood collected in a K2EDTA tube from both recipients and donors using the QIAmp Blood Mini Kit™ (Qiagen, Inc.). Automated DNA sequencing using both commercial (Abbott Molecular Inc., Illinois and QIAGEN Inc., CA) and in house reagents will be used to HLA type the samples. Loci sequenced will included HLA Class I (HLA-A, -B and -C) and HLA Class II (HLA-DRB1/3/4/5, -DQA1 and - DQB1). For Class I, exons 2 and 3 containing the defining polymorphic regions for most alleles will be amplified and sequenced. For Class II, typically only exon 2 will be sequenced. Any sequencing ambiguities will be resolved by sequencing additional exon(s).

### 11.2 T Cell Phenotype and Function

We will use MFC to profile leukocyte subpopulations, determine frequencies of donor-reactive T cells, assess donor-specific suppression by darTregs, and use deuterium labeling and TCR sequencing to track infused darTregs. Together, these assays allow us to assess the impact of darTregs therapy and/or Treg-supportive IS on the alloimmune profile of the patients.

Treg TruCount analysis: One ml of whole blood will be collected at the time points indicated in the SOE. The samples will be used directly for analysis without cryopreservation. Fifty microliters of the blood will be aliquoted into a TruCount tube, stained with fluorochrome-conjugated antibodies to CD4, CD25 and CD127, and analyzed on a flow cytometer to enumerate the numbers of Tregs. This assay would allow us to obtain the absolute Treg counts in one microliter of blood and determine if the counts are altered by darTreg therapy.

Frequency of donor-reactive T cells: We will use the assay described in *Figure 13* to determine the frequency of donor-reactive CD4+ Tconvs, CD8+ T cells, and Tregs at time points indicated in the SOE. We expect to see an increase in darTregs shortly after infusion, especially in the 200 million and 800 million dose cohorts.

[figure not shown]

Figure 13. Assay for measuring frequency of donor-reactive T cells.

In vitro suppression: We will assess suppression by Tregs isolated from patients at time points indicated in the SOE. Pretransplant PBMCs will be used as responders mixed with Tregs from various time points. Tregs will be sorted from frozen PBMCs based on the cell surface phenotype of CD4+CD127lo/-CD25+. PBMC for this assay will be obtained from whole blood on the day of transplantation. The cultures will be stimulated with irradiated donor splenocytes to assess donor-specific suppression and with anti-CD3 and anti-CD28 to assess nonspecific suppression.

MFC panels: We will use MFC to determine the percentages of leukocyte subsets in peripheral blood using panels of antibodies developed in our lab. Panels and markers are summarized in *Table 3. MFC Panel Markers*. Adjustments might be made if future data from other trials are able to better inform the panel selection.

Confidential Page 52 of 80

Table 4. MFC Panel Markers

Panel	Cell #	Markers								
Leukocyte panel	0.25m	CD45	CD14	CD3	CD19	CD56	CD16	CD4	CD8	CD7
Effector/Memory/ Naïve T Cells	0.5m	CD3	CD4	CD8	CD45RA	CD27	CD28	CCR7		
Treg Panel	1m	CD3	CD4	CD25	CD127	FOXP3	HELIOS			
B cells	0.5m	DR	CD19	CD20	CD27	CD38	IgD			

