### **Protocol Synopsis**

	, '
Title	Donor-Alloantigen-Reactive Regulatory T Cell (darTreg) Therapy in Liver Transplantation
Short Title	darTregs in Liver Transplantation (deLTa)
Protocol Number	RTB-002
ClinicalTrials.gov Identifier	NCT02188719
Clinical Phase	Phase I
Safety Objective	This study will evaluate the safety, tolerability, and dose limiting toxicities (DLTs) of a Treg-supportive Immunosuppression (IS) regimen and darTreg infusion for adult, de novo, liver transplant recipients.
Mechanistic Objectives	This study will evaluate 1) the effects of a Treg-supportive IS regimen and Treg infusion on immunological profiles of liver transplant recipients, and 2) explore the hypothesis that ex vivo-expanded darTregs will be biologically active.
Study Design	A multi-center, open-label, dose escalation, pilot trial with four cohorts (Treg-supportive IS only group + three darTreg dosing groups) conducted in a phased schema.
Safety Outcome	The safety, tolerability, and dose-limiting toxicities (DLTs) of darTreg therapy given within the context of a Treg-supportive IS regimen will be evaluated with the rate of the following events within 40 weeks of transplantation.  Clinical outcomes that will be described are:  1. Incidence and severity of biopsy proven acute rejection (AR) and/or chronic rejection (CR)  2. Incidence of ≥ Grade 3 infections as defined in Section 14.3.1  3. Incidence of wound complications (≥ CTCAE Version 4.0, Grade 3)
	
 
4. Incidence of anemia, neutropenia, and/or thrombocytopenia (according to study defined reporting requirements, Section 14.3.1 Grading Criteria)
 
5. Incidence of adverse events (AEs) attributable to the darTreg infusion including infusion reaction / cytokine release syndrome (CRS) (≥ CTCAE Grade 3), and malignant cellular transformation.
 

Mechanistic Outcomes	
 
Treg frequency in peripheral blood using Treg TruCount assay
 
Persistence of infused darTregs in blood and biopsies using deuterium labeling and T cell repertoire analysis
 
darTreg and darTconv frequency in peripheral blood using an in vitro allofrequency assay
 
Multicolor flow cytometry (MFC) to assess effect on immune profiles
 
Functional assessment of Treg in peripheral blood using a mixed lymphocyte reaction (MLR) suppression assay
 
Histology and immunophenotype of liver biopsies
 

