#### **Minimum Circulating Tregs**

We are requiring a minimum threshold of circulating Tregs at the time of recruitment for a practical reason. In order to be able to manufacture a darTreg product, we will need to be able to isolate a sufficient starting population of Tregs from the liver transplant candidate through phlebotomy or leukapheresis. Patients with very low concentrations of Tregs may not yield sufficient Treg numbers to support darTreg production.

After transplantation, we do believe that we need to achieve a dominance of Tregs over Tconvs. We aim to achieve this goal by the combination of depletion and administration of increasing doses of darTregs.

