# 8. Study Mandated Procedures

# 8.1 Leukapheresis or Whole Blood Draw for PBMC Collection

Leukapheresis may be necessary to ensure collection of adequate numbers of autologous Tregs to support ex vivo expansion of darTregs for infusion after liver transplantation, particularly for those enrolled in Cohorts 3 and 4. The study team will make a decision in the best interest of a particular subject based on the current clinical picture including assigned study cohort, peripheral Tregs in circulation, and hemogloblin level. If a subject has a hemoglobin level greater than 10 gm/dL, he or she will have the option to undergo phlebotomy. If the patient has a hemoglobin level less than or equal to 10 gm/dL and remains eligible for the study, the patient will undergo leukapheresis. Number of Tregs in peripheral circulation will also guide decision for method of PBMC collection (leukapheresis or whole blood) where subjects should have at least  $30/\mu$ L peripheral blood Tregs for whole blood collection. For subjects to have whole blood draw, 450-500ml whole blood will be collected.

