In Protocol RTB-002, Tregs from transplant patients will be labeled with deuterium by including the H label in the culture medium during the entirety of the expansion phase in vitro (day 0 to day 14) prior to infusion in the patient. Based on data from in vitro labeling studies, we expect the cells to be ~60% enriched for H. After infusion, PBMCs will be isolated and stored at specified time points as described in the SOE. DNA prepared from these samples will be analyzed by gas chromatography-mass spectrometry. Based on prior studies, we expect sensitivities in the range of approximately ±0.05 to 0.10% enrichment (which refers to the fraction of labeled molecules) (Busch, 2007) (Macallan, 1998). As detailed in Section 1.2.2, we expect the patients to have about 5 x 109 endogenous Tregs 10 to 13 weeks after Thymoglobulin® treatment. Therefore, an infusion of 200 and 800 x 10^6 darTreg in the higher dose groups will likely result in a detectable increase in overall Treg numbers, detectable by TruCount (BD Biosciences) and MFC assays (Section 10.2) at early time points. Deuterium labeling will allow investigators to distinguish between infused darTregs and endogenous Tregs, thus unequivocally demonstrate the presence of infused darTregs in the periphery. Similarly, presence of deuterium-labeled Tregs in the graft will be determined by analyzing genomic DNA extracted from FACS-purified CD4+ cells isolated from biopsy tissues collected at 1 week after darTreg infusion and at the time of rejection. Deuterium labeling will be detectable for at least 4 cell divisions of the administered darTregs. We expect this method of detection to be especially advantageous at early time points (up to 28 days) post infusion, prior to significant division, exit into tissues, and/or loss of darTregs.

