VR Conversion										1						EVI	R target	trouc	h 6-8 µ	a/L 2, !	,	Ť		Ī
darTreg Expansion (Cohorts 2, 3, and 4 Only)										$\top$	1			П					Х	Ĭ1				1
		Local L	aborato	ry Assess	sment	ts																		
Pregnancy Test (Urine or Serum hCG)				2														T			$\overline{}$	7.		
HLA Typing	х																				7	7		1
Viral Serology: HIV Ab, CMV IgG, EBV IgG, HBV (HBsAg, HBcAb, HBeAb, HBeAg, HDVAb), HCVAb3	х																				7	7.		1
/iral Nucleic Acid Testing: HBV DNA (for HBV positive subjects)	х	х																			=	7.		1
Viral Nucleic Acid Testing: HCV NAT (Screen A: most current test within 6 months prior to txp, Screen C: all subjects)	Х			х								х									7	$\overline{}$		1
CBC (with differential and platelets)	х		x 	х		х	х	x	×	х	х	х	х	х	х	x >	( X	х	X	X	X	X	x x	×
CD3 Count					x10	х	х	x x	10									T			7	7		1
CD4 Count												х						T			7	7		
Basic Chemistry (Na, K, Cl, CO2, Creatinine, BUN)	х		x 	х		х	х	x	×	х	х	х	х	х	х	x >	( X	х	X	X	X.	X	x x	×
Liver Function Tests (ALT, AST, Alk Phos, GGT, T Bilirubin, D Bilirubin)	х		x 	х		х	х	x	×	х	х	х	х	х	х	x >	( X	х	X	X	X	X	XX	X
NR/PTT	х		x 	х		х	х	x	×	х	х	х	х	х	х	x )	( X	х	X	X	X	X	XX	x
AFP 	х		x 																		7	7		1
Facrolimus Level									×	х	х	х	Х	х	х	x >	( X	х	X	X	X	$\mathbf{x}$	XX	×
EVR Level 														х	Х	x )	СХ	х	X	X	X	X.	XX	x
Jitrasound and Doppler Examination												х									7	7		1
Jrine Protein/Creatinine Ratio												х									7	7		1
ocal Pathology Results - Graft Routine Histology			x 															x 13	3		1	7		×
		Central I	Laborato	ory Asses	smer	nts																		
rotocol Liver Biopsy																		x 13	3		$\overline{}$			×
reg TruCount (2ml Green Heparin Tube)	2																					$\overline{}$		Collect only w
Allofrequency Assay & MFC-Leukocyte, Treg, Tact/mem, B Cell Panels (10 ml Green Heparin Tube)			10 							$\top$		10						1			7	7		CIB visit
/ILR Suppression Responder Cells (10-10 ml Green Heparin Tubes)			100							$\top$								1			7	7		coincides w
MLR Suppression (2-10ml Green Heparin Tubes)			20 							$\top$		20						1			7	7		scheduled vi
Alloantibody Analysis-Donor HLA Ab (3ml Serum Separator Tube)	1		3 			$\Box$				$\top$							1	$\top$			$\nearrow$	$\nearrow$	$\overline{}$	with central la
and the state of t	2																							

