Allofrequency Assay & MFC-Leukocyte, Treg, Tact/mem, B Cell Panels (10 ml Green Heparin Tube)	10		10				10	Collect only when
MLR Suppression (2-10ml Green Heparin Tubes)	20		20				20	CIB visit coincides
Treg Detection: TCR Sequencing (10ml Green Heparin Tube)	10		10				10	with scheduled
Alloantibody Analysis-Donor HLA Ab (3ml Serum Separator Tube)	3		3				3	visit with central
	43.0		43.0				43.0	

\*\* Corresponds with Cohorts 2, 3, and 4 time points (post drTreg infusion).

<sup>1For each protocol (W12) or clinically indicated biopsy, one specimen will be in formalin for unstained slides, one specimen in PBS for deuterium tracking, and one specimen in RNALater.

<sup>2AFP is only required for subjects known to have HCC.

Confidential Page 77 of 80

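### TruCount, the named assay for mechanistic outcome 1, is scheduled only at Screen A, so the change after darTreg infusion promised in protocol 11.2 cannot be measured with it

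*Protocol*

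**What the plan says.** The synopsis and protocol 3.3 give mechanistic outcome 1 as "Treg frequency in peripheral blood using Treg TruCount assay". Section 11.2 says the assay will "obtain the absolute Treg counts in one microliter of blood and determine if the counts are altered by darTreg therapy", and sets the sampling by reference: "One ml of whole blood will be collected at the time points indicated in the SOE". Section 11.5 expects the 200 and 800 million doses to give a "detectable increase in overall Treg numbers, detectable by TruCount (BD Biosciences) and MFC assays" early after infusion. Section 15.4.4 describes the mechanistic assays as following Treg subsets before and immediately after infusion.

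The schedules give TruCount one entry. Appendix 1 has the row "reg TruCount (2ml Green Heparin Tube" (first letter lost in the text as read), with a 2 in the Screen A column and nothing after it. Appendices 2 to 5 have no such row. Section 12 says TruCount must be run on fresh samples.

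Other text suggests why a count is wanted at Screen A. In 4.1: "We are requiring a minimum threshold of circulating Tregs at the time of recruitment for a practical reason". In 8.1: "Number of Tregs in peripheral circulation will also guide decision for method of PBMC collection".

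**The concern.** The outcome, the assay description and the schedule do not agree. Section 11.2 passes the timing to the schedules, and they call for no TruCount after depletion, at T0, after infusion or in Cohort 1 follow-up. A team following the protocol exactly would have one value per subject, taken before transplant.

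TruCount may have become a screening test for manufacturing feasibility, with outcome 1, 11.2 and 11.5 left unrevised. Either way the passages conflict. What is at stake is the absolute-count answer to whether the infusion changes circulating Treg numbers, and the same answer for the supportive immunosuppression alone in Cohort 1. The separate mechanistic analysis plan announced in SAP section 1, which is not among the documents reviewed, could define a derived count but could not supply fresh samples that were never drawn.

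**Working it through.** **1. Schedules side by side**

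| Schedule | TruCount | Printed central-laboratory total (mL) |
|---|---|---|
| Appendix 1, Stages 1 and 2 | 2 mL at Screen A only | totals line survives only as a 2 in its first cell |
| Appendix 2, Cohort 1 weeks 12, 24, 40 | no row | 43.0 each |
| Appendix 3, T0 / 24 h / days 7, 28, 84 / week 28 | no row | 43.0 / 20.0 / 50.0 each / 53.0 |
| Appendix 4, early termination from Stage 2 | no row | none |
| Appendix 5, early termination from Stage 3 | no row | 53.0 |

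**2. Could a row have been lost when the text was read?** The listed tubes in Appendices 2, 3 and 5 are 10, 20 and 3 mL.

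- Appendix 2: 10 + 20 + 10 + 3 = 43, the printed total.
- Appendix 5: 10 + 20 + 10 + 10 + 3 = 53, the printed total.
- Appendix 3: some cells are garbled. As read they sum to 53, 50, 60, 60, 60 and 53, against printed totals of 43, 20, 50, 50, 50 and 53. The check therefore uses the printed totals. Each can be built from the listed tubes: 4 × 10 + 3 = 43; 2 × 10 = 20; 5 × 10 = 50; 5 × 10 + 3 = 53 (the 20 mL draw is two 10 mL tubes).
- Sums of these tubes end in 0 or 3. An added 1 mL tube would make them end in 1 or 4, and a 2 mL tube in 2 or 5. Every printed total ends in 0 or 3, so no separate TruCount tube is hidden.

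For the later columns of Appendix 1 and for Appendix 4 there are no usable totals, so the reading rests on blank cells and row labels.

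**3. Values not collected**

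- Subjects planned for infusion: Cohorts 2 and 3 have 3 to 6 each and Cohort 4 has 6, so 12 to 18.
- Six central-laboratory visits each: 6 × 12 = 72 to 6 × 18 = 108 possible values, 0 scheduled.
- Cohort 1 follow-up: 3 visits × 6 subjects = 18, 0 scheduled.
- Only the doses and times for which 11.5 expects a rise (Cohorts 3 and 4 at T0, 24 h, day 7 and day 28): 9 to 12 subjects × 4 = 36 to 48, 0 scheduled.

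**4. Can Screen A be the baseline?** Section 1.2.2 gives 13.1 × 10^9 Tregs at the start and 41% of the pre-transplant level after Thymoglobulin.

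- 0.41 × 13.1 = 5.4 × 10^9, the protocol's own figure.
- Fall: (13.1 − 5.4) / 13.1 = 59%.
- Against the highest dose: 7.7 / 0.8 = 9.6 times.

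Expected rise from T0, using 5.4 and the protocol's other endogenous estimates (5 in 11.5, 4 in 1.2.1, all × 10^9):

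| Dose | /5.4 | /5 | /4 |
|---|---|---|---|
| 0.2 × 10^9 | 3.7% | 4% | 5% |
| 0.8 × 10^9 | 14.8% | 16% | 20% |

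Measured from Screen A, the depletion would swamp the infusion effect. The percentages assume that blood counts move in proportion to whole-body numbers, which the documents do not state.

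**5. Room under the blood cap** (9.4.2: 168 mL in eight weeks)

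- T0 + 24 h + day 7 + day 28 = 43 + 20 + 50 + 50 = 163 mL.
- Four 1 mL draws: 163 + 4 = 167 mL. Four 2 mL draws: 163 + 8 = 171 mL, over the cap.

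**The case against.** The best counter-argument is that little is lost. Outcome 1 is worded as a frequency, 11.5 names flow cytometry beside TruCount as a means of detection, and the flow-cytometry Treg panel and CD4 counts are scheduled after infusion and in Cohort 1. The question is therefore largely answerable from samples already planned. That stands as a limit on the consequence. It does not remove the conflict: flow cytometry is listed separately as outcome 4, and nothing names it as the substitute for TruCount.

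The text as read is also imperfect. The totals cannot exclude a small aliquot from a tube already drawn, and the assay uses only 50 microliters. That is fair, but no schedule calls for such an aliquot.

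The count of 72 to 108 includes Cohort 2, for which no rise is predicted; 50 million cells would add only about 0.9% (0.05/5.4) to 1.3% (0.05/4). The narrower count is 36 to 48, still with none scheduled. A rise of 4 to 5% in 3 to 6 subjects may not be visible even with TruCount, since no assay variability is given. This weakens the case for new draws at that dose, and leaves the text needing correction.

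Finally, the cap arithmetic covers central tubes only. Local tests such as CD4 count and CMV/EBV DNA have no stated volume. If any of these are research draws, a 1 mL margin does not prove compliance. That stands.

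**Conclusion.** The concern holds. As written, TruCount gives one pre-transplant value and none after Thymoglobulin, at T0, after infusion or in Cohort 1 follow-up, so the comparison promised in 11.2 cannot be made with the assay named for it. This is firm for Appendices 2, 3 and 5, where row labels and totals agree, and rests on blank cells or missing rows for Stage 2 and Appendix 4.

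It should be corrected but is not critical. The outcome is exploratory; flow cytometry, deuterium and TCR tracking remain; and no safety or dose-escalation decision uses TruCount.

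**What to change.** Choose one and make the synopsis, 3.3, 11.2, 11.5 and the schedules agree.

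**(a) Redefine the outcome.** Define outcome 1 as local CD4 count × Treg fraction of CD4 cells from the flow-cytometry Treg panel, at T0, days 7, 28 and 84 and week 28 after infusion, and at weeks 12, 24 and 40 in Cohort 1. State that TruCount is for screening only. First confirm in the source Appendix 3 that the flow-cytometry tube is drawn at T0: the printed 43.0 mL is 10 mL below the cells as read, and does not show which tube is absent. Include 24 h only if the tube is confirmed there too (printed total 20.0 mL). Cost: wording only, if those tubes are confirmed. The price is a count built from two platforms, less precise than TruCount.

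**(b) Schedule the assay.** Add TruCount at T0 and the existing post-infusion central-laboratory visits in Appendix 3, and at the matched Cohort 1 visits in Appendix 2. Use a fresh 50 microliter aliquot of a tube already drawn, or a 1 mL draw. Settle the volume, since 11.2 says 1 mL and Appendix 1 a 2 mL tube, and check it against the 168 mL cap with any local research draws counted. The aliquot avoids the cap question. Cost: a schedule amendment, assay charges and same-day handling. Cohort 1 follow-up has no deuterium blood tube, so fresh-blood handling must be arranged at those visits, although the Screen A row has no cohort restriction and the route may partly exist.
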